5.1.1 Retesting During Screening

Retesting of laboratory parameters and/or other assessments during the Screening period will not be permitted, except PT, aPTT and INR (this does not include parameters that require a confirmatory result).

Any new result will override the previous result (ie, the most current result prior to randomization) and is the value by which study inclusion will be assessed, as it represents the subject's, most current clinical state.

5.2 Study Materials

BMS will supply the sites with the following materials:

- Electronic case report forms (CRFs)
- BMS SAE electronic CRF Form
- BMS Pregnancy Surveillance Form
- Adjudication binder and worksheets
- Mandatory Patient diary for study medication, date and time of doses completed daily by patient/ parent or study staff.
- Laboratory manual

5.3 Safety Assessments

Informed consent must be obtained prior to any study screening procedures that would not have been performed as part of normal subject care. Screening activities should be conducted within 14 days prior to randomization to either thromboprophylaxis with apixaban or no thromboprophylaxis.

A platelet count should be performed within 24 hours prior to the start of apixaban therapy.

End of treatment visit must be completed on Day 29 \pm 5 days of induction chemotherapy and will be performed after:

- Completion of approximately 28 days of induction chemotherapy in subjects.
- Subject withdrawal from the study as per any of the reasons listed in [Section 3.5](#).

Any additional medical testing and procedures, whether more frequent or in addition to those described, should be performed as medically indicated.

Any safety events occurring after consent and up to Day 35 \pm 5 should be sent for adjudication.

5.3.1 Bleeding Assessment

Major bleeding is defined as bleeding satisfies one or more of the following criteria: (i) fatal bleeding; (ii) clinically overt bleeding associated with a decrease in Hgb of at least 20 g/L (2 g/dL) in a 24 - h period; (iii) bleeding that is retroperitoneal, pulmonary, intracranial, or otherwise involves the central nervous system; and (iv) bleeding that requires surgical intervention in an operating suite (including interventional radiology).

Clinically relevant non-major bleeding is defined as bleeding satisfies one or both of the following: (i) overt bleeding for which a blood product is administered and which is not directly attributable to the patient's underlying medical condition and (ii) bleeding that requires medical or surgical intervention to restore hemostasis, other than in an operating suite.

Minor bleeding: is defined as any overt or macroscopic evidence of bleeding that does not fulfill the above criteria for either major bleeding or clinically relevant, non-major bleeding.

Menstrual bleeding resulting in a medical consultation and/or intervention will be classified as a minor bleeding event.

All bleeding events and their supporting documentation **MUST** be sent for adjudication.

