4.2 Secondary Endpoints

Efficacy:

- a) Non-fatal asymptomatic DVT
- b) Non-fatal symptomatic DVT
- c) Non-fatal PE

- d) CVST
- e) VTE-related-death

Safety

[figure not shown]
- a) Composite of major and CRNM bleeding

[figure not shown]
CRNM bleeding is defined as bleeding that satisfies one or both of the following:

- 1) overt bleeding for which blood product is administered and not directly attributable to the subject's underlying medical condition and
- 2) bleeding that requires medical or surgical intervention to restore hemostasis, other than in an operating room

Pharmacokinetics and Anti-FXa Activity

- a) Apixaban pharmacokinetics using a population pharmacokinetic (PPK) approach
- b) Anti-FXa activity

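### Protocol 5.3.1 makes all treated menstrual bleeding minor, although some of it meets the CRNM or major definition, and the endpoint sections of both documents carry no such exception

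*Protocol*

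**What the plan says.** Protocol 5.3.1 sets out three classes of bleeding. Major bleeding includes, under (ii), overt bleeding with a haemoglobin fall of at least 20 g/L within 24 hours and, under (iv), bleeding that needs surgery in an operating suite. CRNM bleeding includes, under (i), "overt bleeding for which a blood product is administered and which is not directly attributable to the patient's underlying medical condition" and, under (ii), "bleeding that requires medical or surgical intervention to restore hemostasis, other than in an operating suite". Minor bleeding is the residual class, namely overt bleeding that "does not fulfill the above criteria for either major bleeding or clinically relevant, non-major bleeding".

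The next sentence reads: "Menstrual bleeding resulting in a medical consultation and/or intervention will be classified as a minor bleeding event". It has no qualifier.

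Protocol 8.3.1 and 8.3.2 and SAP 4.1 and 4.2 repeat the major and CRNM criteria as endpoint definitions. SAP 4.2, for example, counts "bleeding that requires medical or surgical intervention to restore hemostasis, other than in an operating room". None of these sections mentions menstrual bleeding, and none defines minor bleeding. Protocol 8.3.1 and SAP 4.1 send all bleeding to a blinded committee, which assigns one of the three classes.

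**The concern.** A residual class cannot also contain events that meet the criteria of a higher class. The menstrual sentence puts them there, because the word intervention carries no limit on severity or purpose. The committee then has two rules for one event, and neither document says which governs.

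The affected endpoints are the primary safety endpoint (major bleeding) and the secondary one (major plus CRNM). Eligibility covers females up to 17 years, and Protocol 3.4.2 accepts that apixaban may raise the likelihood of bleeding, so events of this kind can be expected to arise. The class label is also used elsewhere: Protocol 3.5 lists a major bleed among the reasons for discontinuation, and Table 5.3.2-1 has a separate row for minor bleeding. Those passages also need one unambiguous classification to refer to.

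**Working it through.** **Step 1: the definitions side by side.** No calculation is needed to establish the conflict.

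| Menstrual bleeding event | Class by the general criteria | Class by the menstrual sentence | Conflict |
|---|---|---|---|
| Consultation only, no major or CRNM criterion met | Minor | Minor | No |
| Treated, but treatment not needed to stop the bleeding, no other criterion met | Minor | Minor | No |
| Treatment needed to stop the bleeding, outside the operating suite | CRNM (ii) | Minor | Yes |
| Blood product given, bleeding not attributed to the underlying disease | CRNM (i) | Minor | Yes |
| Treated, with a haemoglobin fall of at least 20 g/L in 24 hours | Major (ii) | Minor | Yes |
| Operating-suite procedure needed | Major (iv) | Minor | Yes |

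The general criteria are those in Protocol 5.3.1 itself, repeated in Protocol 8.3.1/8.3.2 and SAP 4.1/4.2. The conflict is therefore inside 5.3.1, and between 5.3.1 and the endpoint sections of both documents.

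**Step 2: the plan's own figures.** The documents give no bleeding rate, no menstrual-bleeding rate and no power for safety. The only power statement concerns efficacy. With the pooled-variance Pearson chi-square at one-sided 0.025, it reproduces: 250 per arm at 17% versus 8.5% gives 81.5%, and 200 per arm (after 20% exclusion) at 20% versus 10% gives 80.2%. Both exceed the stated 80%. Neither depends on how bleeding is classified, so the sample size is not affected.

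**Step 3: illustration of size.** Everything except n is an assumption, not a figure from the documents.

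- n = 500 / 2 = 250 per arm (Protocol 8.1).
- f = share of subjects who menstruate: 5% to 15%.
- q = proportion of those with menstrual bleeding that needs intervention: 2% to 10% on control and 4% to 20% on apixaban, a ratio of 2 by assumption.
- Subjects moved to minor = n × f × q.

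Control: 250 × 0.05 × 0.02 = 0.25, up to 250 × 0.15 × 0.10 = 3.75. Apixaban: 250 × 0.05 × 0.04 = 0.5, up to 250 × 0.15 × 0.20 = 7.5. As f × q, this is 0.1 to 1.5 percentage points on control and 0.2 to 3.0 on apixaban.

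**Step 4: effect on the comparison.** Assume other major or CRNM bleeding at 5% on control and 8% on apixaban, with no overlap with the menstrual events.

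- Menstrual events left out: relative risk 0.08 / 0.05 = 1.60; difference 3.0 points.
- Counted, low end: 0.082 / 0.051 = 1.61; difference 3.1 points.
- Counted, high end: 0.110 / 0.065 = 1.69; difference 4.5 points.

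With background rates of 2% and 4%, the relative risk is 2.0 either way, because the assumed menstrual ratio is also 2. The difference is 2.0 points with the events left out and 2.1 to 3.5 with them counted.

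**Step 5: direction.** The relative risk with the events counted is a weighted average of the background and menstrual relative risks, so the direction depends on which is larger. Suppose menstrual bleeding were equally frequent in both arms, with f = 10% and q = 5%. Each arm then gains 0.5 points when these events are counted, and the relative risk is 8.5 / 5.5 = 1.55. Leaving them out gives 1.60, so here the menstrual rule would raise the relative risk, with the difference unchanged at 3.0 points.

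**The case against.** A reader might infer that the trial will under-count a likely harm of apixaban and bias the bleeding comparison toward no difference. The documents do not support that, for four reasons.

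- The loss is conditional. If the committee applies Protocol 8.3 and SAP 4, these events count as CRNM or major. The adjudication charter is not among the documents.
- The direction is not established. The documents speak of bleeding risk in general and say nothing specific about menstrual bleeding. Step 5 shows that the relative risk could move either way.
- The events stay visible. SAP 7.6.1.2 gives minor bleeding its own rate, relative risk, interval and nominal p-value, and lists all bleeding. SAP 7.6.2 summarises bleeding-related adverse events by preferred term and arm. The bleeding p-values are nominal, so no confirmatory conclusion turns on this.
- Not every treated or transfused case is affected. Treatment is a wider notion than treatment needed to stop bleeding, and CRNM (i) excludes bleeding attributed directly to the underlying disease, a real limit in leukaemia.

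A reader might also take this as protocol against SAP. That is not so: Protocol 8.3 omits the menstrual rule just as the SAP does, and the SAP is silent on menstrual bleeding rather than contradictory.

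Finally, the sentence may be meant only to explain the minor class, or may be a deliberate convention. Protocol 8.3.1 says its endpoints agree with a society recommendation, which cannot be checked here. Either is possible, but neither removes the defect. An explanatory sentence should not extend beyond the class it explains, and a deliberate exception belongs in the endpoint definitions.

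**Conclusion.** The inconsistency is real and needs no assumption: Protocol 5.3.1 assigns to minor some events that its own definitions, and the endpoint sections of both documents, assign to CRNM or major. Menstrual bleeding that leads only to a consultation and meets no higher criterion is minor under every section and is not affected.

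The consequence is conditional. If 5.3.1 is applied literally, qualifying events leave both the primary and the secondary safety endpoint. Size and direction cannot be derived from the documents. The figures of about 0.5 to 7.5 apixaban and 0.3 to 3.8 control subjects per 250 rest wholly on the assumed shares and rates in step 3. On those assumptions the relative risk barely moves, while the risk difference falls by 0.1 to 1.5 points. The effect is probably small. The reason to act is that a safety endpoint should have one definition and the correction is cheap.

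**What to change.** Choose one of two routes.

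1. Limit the menstrual sentence in Protocol 5.3.1 to menstrual bleeding that meets no major or CRNM criterion.
2. If the exception is deliberate, state it in Protocol 8.3.1/8.3.2 and SAP 4.1/4.2, amend the residual definition of minor bleeding to allow for it, and add a sensitivity analysis of both safety endpoints that classifies these events by the general criteria.

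On either route, use identical text in Protocol 5.3.1, Protocol 8.3, SAP 4 and the adjudication charter.

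The first route costs one sentence. The second adds a small sensitivity analysis, for which the committee must also record the class each menstrual event would have had by the general criteria. Sample size and efficacy power do not change. The downside is that the reported CRNM or major rate may rise slightly.

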5.3.2 Treatment guidelines for Bleeding / Suspected Bleeding

[figure not shown]
Patients with bleeding or suspected bleeding should undergo confirmatory laboratory or other testing as indicated clinically (eg, compression Ultrasound (US), Computer Tomography (CT), Magnetic Resonance Imaging (MRI)). The date and time of the onset of the bleeding event will be recorded on the CRF. The following routine measures may be considered:

Table 5.3.2-1: Treatment Guidelines for Bleeding / Suspected Bleeding

Minor Bleeding	Apixaban may or may not be held based on an individualized benefit-risk assessment
Clinically Significant Bleeding	
Apixaban should be held if subject meets criteria outlined in section 3.5.
 
 Identify of the source and institute local measures to stop the bleeding. Perform laboratory test monitoring (eg, hemoglobin, INR, aPTT, platelet count, anti-Factor Xa activity). Apixaban may be best monitored using an anti-Factor Xa assay rather than the more standard coagulation tests (eg, INR, aPTT) which are less sensitive to apixaban. If bleeding occurs up to 6 hours after apixaban administration consider administration of activated charcoal oral solution to reduce apixaban plasma exposure. Consider appropriate symptomatic treatment (eg, mechanical compression, surgical intervention, fluid replacement and hemodynamic support, blood product or component transfusion) For bleeding that does not respond to local measures, consider administration of fresh frozen plasma (FFP) as a supportive measure, recognizing that FFP does not reverse the anticoagulant effects of apixaban
Life Threatening Bleeding	
Apixaban should be held for all life threatening bleeding or if subject meets criteria outlined in section 3.5.
 
 Administration of recombinant Factor VIIa may be considered, however, there is no experience with this agent in apixaban-treated patients. Its effectiveness for counteracting the effects of apixaban is not known. Activated prothrombin complex concentrate (aPCC) or prothrombin complex concentrate (PCC, also referred to as factor IX concentrate) are other procoagulants that may be considered, but considering the variety of formulations available and the complexity of dosing, the decision to employ aPCC or PCC should be made by an experienced clinician with careful evaluation of the risks and benefits. If bleeding occurs up to 6 hours after apixaban administration activated charcoal oral solution administration may be considered in order to reduce apixaban plasma exposure.

- Delay the next dose of study drug or discontinue study medication if indicated
- Fluid resuscitation and blood transfusion as indicated
- Fresh frozen plasma or general hemostatic measures as indicated
- There is no specific reversal agent for apixaban approved in the pediatric population

Table 5.3.2-1 provides information for the treatment of bleeding or suspected bleeding. The specific treatment for bleeding is left to the discretion of the investigator and/or the attending physician based on the medical status of the subject and/or institutional policies.

5.3.3 Laboratory Assessments

Blood samples will be obtained on selected visits of clinical laboratory evaluations as outlined in [Section 5.1](#) ([Table 5.1-1](#) and [Table 5.1-2](#)- Flow chart/ Time and Events Schedule). A local laboratory should perform the analyses and will provide reference ranges for these tests. The following laboratory tests are required for this study, and should be analyzed by the local laboratory: CBC with platelets, serum creatinine, ALT, AST, and Conjugated Bilirubin, WBC and RBC in CSF (WBC at Day 1 Screen only), PT (if available), aPTT, INR (or thrombin time or Reptilase) and pregnancy test when applicable. The PK and PD assessment will be analyzed by a third party laboratory. For these laboratory assessments, materials and detailed instructions for specimen collection, processing, storage and shipment will be provided in special kits and will be described in a separate laboratory manual.

5.3.4 Pregnancy tests

For females of reproductive potential (FRP), a serum or urine pregnancy test should have a minimum sensitivity of 25 IU/L or equivalent units of β HCG. All on-study pregnancy testing should follow the schedule detailed in [Table 5.1-1](#).

5.3.5 Creatinine Clearance

Based on the results of the enrollment visit clinical laboratory tests, eGFR will be estimated based on the Schwartz formula (See [Table 5.1-1](#) for timing of assessments and [Appendix 13](#) for eGFR assessment).

Inadequate Renal Function < 30% of normal for age and size as determined by the Schwartz formula⁶⁸ [eGFR (ml/min/1.73m²) = 0.413 * (height (cms) / serum creatinine (mg/dl)). If serum creatinine concentration is measured in SI units (umoles/L), divide this number by the conversion

factor of 88.4 to get the SI units (mg/dl) before inserting into the Schwartz formula to calculate eGFR]. Subjects are required to have an eGFR > 30% of normal for age and size to be enrolled in the study.

5.3.6 Physical Examination

A full physical examination should include general appearance, head, eyes, ears, nose, throat, neck, cardiovascular, lungs, abdomen, lymph nodes, extremities, neurological, skin, musculoskeletal, vital signs (heart rate, respiratory rate, blood pressure), height and weight, as well as assessment of central nervous system status (CNS 1, CNS2, CNS 3).

A targeted physical examination should include any organ systems pertinent to the subject's signs, symptoms, or adverse events, such as assessment of signs of venous thromboembolism or bleeding.

Only Investigators licensed to conduct physical examinations and who are listed on the Delegation of Authority Form are approved to perform physical examinations.

5.3.7 Treatment Guidelines for Thrombocytopenia

The platelet count should be $\geq 20 \times 10^9$ per L within 24 hours of starting apixaban. There are no evidence-based guidelines for anticoagulation therapy in relation to platelet counts. In the absence of any other coagulopathy, the following guidelines are recommended during the course of the study period:

- Full-dose apixaban therapy for patients with platelet count $\geq 20 \times 10^9$ per L.
- Hold apixaban for platelet count $< 20 \times 10^9$ per L and restart when platelet count $\geq 20 \times 10^9$ per L or presumed to be above this threshold following a platelet transfusion.

It is important to maximize the thromboprophylaxis therapy. In some circumstances, physicians may choose to give platelet transfusions prior to anticoagulation to maximize the anticoagulation in patients with thrombocytopenia. If at all possible, it is preferred to have as much uninterrupted anticoagulation as possible during the treatment period. A close monitoring of platelet count and careful watching for signs of bleeding are necessary. For subjects with a platelet count $< 20 \times 10^9$ per L or with platelet counts anticipated to drop to below 20×10^9 per L, the platelet counts should be checked at least twice a week and apixaban should be re-started only after platelets are $\geq 20 \times 10^9$ per L OR after a platelet transfusion that is predicted to increase the platelet count beyond this threshold.

5.4 Efficacy Assessments

The primary efficacy assessment of the study is a composite of non-fatal asymptomatic and symptomatic DVT, PE, and CVST; and VTE-related-death objectively confirmed by independent adjudication. All components of the primary efficacy endpoint will be adjudicated by a blinded, independent adjudication committee.

Any suspected efficacy clinical events occurring after consent and up to Day 35 ± 5 should be sent for adjudication.

Details for the assessment of the components of the primary efficacy endpoint are provided in [Appendices 3, 4 and 5](#).

5.4.1 Imaging assessment for the study

On Day 29 \pm 3 days, the imaging evaluation will occur **for all** randomized subjects who remain on protocol therapy. **For subjects in the apixaban treatment arm, Doppler ultrasound and echocardiogram should be performed within 3 days (not exceed 5 days) after termination of the study medication including early discontinuation. For those subjects randomized to the standard of care arm, imaging evaluations will be performed within 3 days but no more than 5 days from the Day 29 visit or early discontinuation from the study.**

The evaluation will include a bilateral Doppler ultrasound that will include imaging of the venous system in which the CVAD is placed and an echocardiogram to assess for right atrial thrombi according to the protocol guidance in [appendices 1 and 2](#). The Doppler ultrasound should be performed for both the ipsilateral (extremity in which the CVAD was placed) and the contralateral sides whenever possible. If there is a difficulty in performing the imaging procedure, Doppler ultrasound from the ipsilateral side alone is acceptable (see [Appendix 1](#) for detailed guidance). Subjects will not undergo routine radiologic screening for CVST.

A chest X-ray is not mandated by the study. However, if a chest X-ray has been performed as part of the standard of care, the chest X-ray should be submitted as part of the adjudication package.

